### Run-in period

The study will start with a 12-week run-in period. Subjects will have either been treated or untreated with a PPI prior to entering this phase of the study. The subjects will receive both oral and written subject information and sign a consent form. At visit 1 all subjects will undergo a physical examination, including vital signs and demographics. Medical and surgical history, especially for GERD will be recorded.

All subjects will attend an "Investigational week". This "week" will allow the collection of baseline data, such as endoscopy with biopsy sampling, 24-hour pH metry, manometry, SAP and laboratory measurements. A 24-hour pH metry performed within 12 months prior to enrolment could be accepted, if made according to the method stated i.e. no antisecretory medication 7 days prior to investigation. Manometry will only be performed at the first occasion of pH metry in all subjects.

The "investigational week" can take place either immediately or 6 weeks after treatment with esomeprazole 40 mg o.d. depending on:

- Whether the subject was treated or untreated with PPI prior to enrolment
- Whether the clinic can offer 24 hr pH metry and SAP within 2 weeks from visit 1 for the untreated subjects.

Esomeprazole must be withheld at least 7 days (visit 2) prior to the "Investigational week".

Dose adjustments are not allowed during the run-in period.

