### **Subjects treated with PPI prior to study start will be treated in one of two ways depending on:**

- (i) if the subject is known (endoscopically) to the investigator prior to entry into the study. These subjects need not undergo an endoscopy at visit 1, but will receive esomeprazole 40 mg o.d. and continue with visit 2 and 3 as scheduled.
- (ii) if the subject is referred to endoscopy, the subject will undergo endoscopy at visit 1 and receive esomeprazole 40 mg o.d. and continue with visit 2 and 3 as scheduled.

The “Investigational week” will take place during visit 3. In case of mucosal breaks classified as LA grade C or D at visit 3 a new endoscopy must be done at visit 4 prior to randomization to exclude the presence of LA C or D at randomization.

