**Subjects untreated with PPI prior to study start will (if possible):**

- (i) start the run-in period with the “investigational week” at visit 1. In such cases an endoscopy with biopsy sampling will be made at visit 1. If insufficient biopsies have been taken at visit 1 then another endoscopy with biopsy sampling will be done at visit 3. In cases of mucosal breaks classified as LA grade C or D at visit 1 or 3 a new endoscopy must be performed at visit 4 prior to randomization. Furthermore, laboratory measurements, 24 hr pH metry, manometry and SAP will be made. If these assessments can be made within 2 weeks from visit 1 then visit 2 and 3 can be left out. The study drug (esomeprazole 40 mg o.d.) will then be dispensed and the subject will continue the run-in period. If the time between first endoscopy (visit 1) and the 24 hour pH metry is more than 2 weeks, the study drug must be dispensed at visit 1 and the subject will follow the same routine as the **treated subject (i)**.

10-year study period

If reflux esophagitis LA grade C or D is found at visit 3, a new endoscopy must be done at visit 4 prior to randomization.

- Subjects will be randomized to either medical treatment or surgery at visit 4. Medical treatment is 20 mg o.d. (start dose) and can be adjusted, but is not to exceed 40 mg daily. Surgery must be performed within 3 months after randomization. The subject is allowed to be treated with esomeprazole 20 mg o.d. and can be adjusted, but is not to exceed 40 mg daily whilst awaiting the surgery. Visit 5 and 6 will only be attended by subjects randomized to surgery.
- Endoscopy with biopsy sampling will be performed at visit 8, 12, 16, 33 and 39. A 24 hour pH metry and SAP will be performed at visit 7 and 16. Endoscopy will be performed at extra visits in case of symptomatic relapse or early discontinuation. A 24 hr pH metry and SAP should be performed in case of dose adjustments (prior to).
- Symptoms will be assessed at each visit except at visit 5 and the telephone visits (visit 30, 32, 34, 36, 38). Laboratory screen will be done at visit 8, 12, 16, 33 and 39 and at early discontinuation visits.
- Patient reported outcomes (PRO) will be assessed by QOLRAD and GSRS at visits 4, 8, 10, 12, 14, 16, 31, 33, 35, 37 and 39 and at early discontinuation visits.
- Body weight will be assessed at visits 4, 8, 12, 16, 33, 39 and at extra visits and at early discontinuation visits.

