- 10 Only for subjects with RE LA grade C or D at visits 1 or 3.
- 11 Only body weight
- 12 30 days after visit 5 (surgery)
- 13 Only for subjects in the surgical arm receiving esomeprazole
- 14 Only for subjects in the medical arm
- 15 In case of administration of healing dose (esomeprazole 40 mg o.d.)
- 16 In case of dose adjustment
- 17 In case of premature discontinuation after randomization (visit 4)

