**Table 3 Efficacy objectives and endpoints relating to each objective**

Objective	Endpoint(s)	Summary statistic for analysis (incl. timepoint and population)	Planned analysis	Significance of results
Primary				
4.1, 4.3.2 To compare treatments with regard to treatment failure	Number of days, treatment failure (yes/no)	Median number of days  ITT population	Logrank test, and survival curves	Longer time to treatment failure indicates a more efficient treatment
Other				
4.3.3 Histopathological findings	Histological assessments .	All histological presentations will be performed for the safety population and ITT population.	No formal statistical comparison	
4.3.4 Periodic prevalence of endoscopic and symptomatic recurrences	Endoscopic relapse (LA grade C-D) between scheduled endoscopies. Symptomatic relapse between scheduled visits	Mean number of relapses per time period (subject year). ITT population	Descriptive descriptive	
4.3.4 Point prevalence of endoscopic and symptomatic recurrences	Endoscopic relapse (LA C-D) at scheduled endoscopies. Symptomatic relapse at scheduled visits.	Mean number of relapses per scheduled endoscopy visit. ITT population		
4.3.5 GI symptoms assoc. with GERD over time	Symptom assessments at clinical visits	Proportion of subjects with no symptoms ITT population	descriptive	
4.3.6 Per-operative events	Per-operative event assessments during the operation	Proportion of subjects randomized to surgery with per-operative symptoms ITT population	descriptive	
4.3.7 Post-operative symptoms and events	Post-operative symptom assessments during the first 30 post-operative days	Proportion of subjects randomized to surgery with post-operative symptoms ITT population	descriptive	
4.3.8 24 hr intragastric and intraesophageal pH	% of time with intragastric and intraesophageal pH $\leq$ 4	ITT population	Descriptive	
4.3.8 Symptom Association Probability (SAP)	Association between symptoms and reflux episodes	ITT population	Descriptive	

The methods for collecting efficacy data are presented below.

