#### **4.3.3 Histopathological changes**

##### **4.3.3.1 Methods of assessment**

Histopathological changes will be assessed by observing the biopsy specimens taken during endoscopy. The biopsy specimens will be sent to a central laboratory with courier. The Central laboratory will send all biopsies for analyses to the pathologist, . A short diagnostic report will be sent to the investigator by fax or email. In addition, the grading of the histological parameters and a full report will be sent to AstraZeneca.

In case of endoscopic suspicion of malignancy, additional biopsies, outside of this protocol should be taken and sent to the local pathology department of each hospital or institute.

Biopsy sampling, handling and logistics will be found in Appendix H.

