### **4.4 Safety measurements and endpoints**

In this study will long-term treatment of esomeprazole be compared to anti-reflux surgery in the control of gastroesophageal reflux disease. The study is designed to study histological findings and changes in laboratory variables and not adjusted for non-serious reporting. The time between visits is too long to receive quality data for non-serious adverse events. The following safety variables will be recorded during the study:

- Histopathological changes in the squamous epithelium of the distal esophagus, the mucosa of the z-line and of the gastric mucosa as assessed by the use of the Sydney classification system (see Section [4.3.3](#) and appendix H)
- Changes in the laboratory screen variables (including serum gastrin, serum chromogranin A, Vitamin B12 and homocysteine)
- All serious adverse events and those adverse events causing premature discontinuation of study drug and/or study.

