### **6.2.3 Statistical analyses**

The two treatment groups will be compared regarding the primary endpoint using Life Table methods for graphic presentation and a log rank test (two-sided) for statistical inference. In both the ITT and the PP analyses data will be censored in case of discontinuation due to reasons other than treatment failure. Post-operative complications, histopathology, endoscopy and symptoms are summarized using frequency tables.

For subjects randomized to the surgery group, post-operative complications during the first month after surgery will be assessed descriptively. Quantitative data on post-operative complications will be tabulated with Mean, SD, min and max. For post-operative complications data with nominal or ordinal outcome, the number of subjects and relative frequency distribution will be presented.

Histopathological changes will be assessed by frequency tabulation by treatment group and visit.

The number of endoscopic and/or symptomatic relapses at clinical visits will be presented by visit and treatment group with frequency tables. Mean, SD, min and max, both combined and separately.

Number of endoscopic and/or symptomatic relapses between visits will be presented by time period (subject year) and treatment group with frequency tables. Mean, SD, min and max, both combined and separately.

GI symptoms associated with GERD over time will be presented by visit and treatment in frequency tables and as number and proportion of subjects with no symptoms.

The percentage of 24 hr intragastric pH  $\leq 4$  will be presented using descriptive methods (Mean, SD) by visit and treatment group.

Symptom Association Probability (SAP) will be presented using descriptive methods (Mean, SD) by visit and treatment group.

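### Section 6.2.3 plans histopathological changes as frequencies by arm and visit, without the within-subject comparison to baseline that it plans for laboratory data

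*Protocol*

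**What the plan says.** The method for histology is one sentence in Section 6.2.3: "Histopathological changes will be assessed by frequency tabulation by treatment group and visit". The same section groups histopathology with endoscopy, symptoms and post-operative complications as data for frequency tables. Table 3 adds populations and rules out a formal comparison: "All histological presentations will be performed for the safety population and ITT population". Section 4.3.3.2 marks endpoint derivation as not applicable, so no change category is defined there.

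Histology has two roles. Table 3 places it among the efficacy objectives. Section 4.4 names it first among the safety variables: "Histopathological changes in the squamous epithelium of the distal esophagus, the mucosa of the z-line and of the gastric mucosa as assessed". That section also explains that visits are too far apart for good data on non-serious adverse events.

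For laboratory variables, the safety analyses in Section 6.2.3 plan the change from baseline to last visit, a cross-table of baseline class against last-visit class, and graphs of last value against baseline. Section 4.4.3.1 fixes the laboratory baseline as visit 3, or visit 1 for untreated subjects.

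After randomization, biopsies are scheduled at visits 8, 12, 16, 33 and 39 (Section 3.1), and another set is required at discontinuation (Section 3.3.5.4). Section 4.3.3.1 says that "the grading of the histological parameters and a full report will be sent to AstraZeneca", so the material for a paired summary is already collected.

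**The concern.** A frequency by arm and visit is a marginal summary. It gives the share of biopsied subjects with a given grade at that visit, and it does not link a subject's grade to that subject's own baseline. This has two consequences.

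First, offsetting movement is invisible: the same frequency at two visits fits no change in anyone, and it also fits many subjects worsening while as many improve.

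Second, the set of subjects biopsied changes over time, and not by the same rule in each arm. Treatment failure is a reason for discontinuation (Section 3.3.5.1). Under Section 6.2.2, a surgical subject fails once symptom control is insufficient and regular drug treatment is needed, and can also fail through post-fundoplication complaints or dysphagia. A medical subject on the starting dose first passes through two dose adjustments. If lesions are related to failure, the arms' later frequencies can diverge with no difference in what happened to any subject's mucosa.

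What is at stake is the reading of graded mucosal change over 10 years, below the level of a serious adverse event. The primary analysis, the sample size and the reporting of serious findings (Section 4.4.2.2) are not affected.

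**Working it through.** The protocol gives no figure for lesion prevalence or for its link to failure, so there is no histology figure to reproduce. The inputs it does give are in Section 6.1: 275 subjects per arm and a 5-year success rate of at least 70%. They agree with the precision stated there: 1.96 × √(2 × 0.70 × 0.30 / 275) = 0.0766, or 7.7 points, within the stated 8. Everything below on prevalence is assumed.

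**1. Offsetting change.** Assume 20% abnormal at baseline and at follow-up, with all 275 biopsied: 0.20 × 275 = 55 abnormal each time. The number newly worsened can be anything from 0 (the same 55 subjects) to 55 (all 55 improved and 55 others worsened). The by-visit table is identical in both cases; a paired table separates them.

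**2. Changing composition at visit 16.** Assume 70% success (the lower end of the protocol's assumption, so 30% failure is its maximum), no other losses, 10% prevalence at baseline and no change in any subject.

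- Retained: 275 × 0.70 = 192.5. Failed: 82.5. Lesions at baseline: 27.5.
- Frequency among attenders = (27.5 − p × 82.5) / 192.5, where p is the prevalence among failures.

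| p | Frequency at visit 16 |
|---|---|
| 5% | 23.375 / 192.5 = 12.1% |
| 10% | 19.25 / 192.5 = 10.0% |
| 15% | 15.125 / 192.5 = 7.9% |
| 20% | 11.0 / 192.5 = 5.7% |

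The row p = 10% is the case of no link between lesions and failure, and the distortion there is zero.

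**3. Changing composition at visit 39.** Assume in addition that the same failure rate continues: 275 × 0.70² = 134.75 retained, 140.25 failed. The frequency is (27.5 − p × 140.25) / 134.75 = 15.2%, 10.0% or 4.8% for p = 5%, 10% or 15%. The 49% retention is an extrapolation that the protocol does not make.

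In steps 2 and 3 a paired table would show no change, by construction, since none was assumed. The steps show only that the marginal table can move when no subject does.

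**4. Coverage of a paired table.** Under the assumptions of step 2, baseline against visit 16 holds at most 192.5 subjects per arm. Baseline against the last available biopsy can hold up to 275, adding up to 82.5 (30%) if the discontinuation biopsies are taken.

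**The case against.** The strongest reply is that this is detail for the statistical analysis plan. Section 6.2.1 promises a comprehensive one before database lock, frequencies by arm and visit are a legitimate summary, and nothing says that no other table will be made. The word *changes* might even cover change categories. Part of this stands: a later plan could add shift tables, and the by-visit tables are not wrong. But the protocol does not leave the histology method open. It states it, and at the same level of detail it gives the laboratory data a within-subject comparison. Table 3 words the objective as findings, and Section 4.3.3.2 derives nothing, so a reading as change categories has little support.

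A second reply is that histology is mainly an efficacy variable and is handled like endoscopy and symptoms. It is indeed absent from Table 4 and from the safety list in Section 2.2. Section 4.4 nevertheless names it as a safety variable, and the limit of a marginal table is the same under either label.

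A third reply is that leavers are not lost to view, because Tables 1 and 2 have a discontinuation column with biopsies. This stands in part. If every leaver were biopsied, adding that column to the attenders would recover the net frequency (in step 2 with p = 15%, 15.125 + 12.375 = 27.5, again 10% of 275). It would still not show who worsened and who improved, and the planned table does not combine the two.

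A reader might also infer that tabulating by visit splits the baseline into a visit 1 row and a visit 3 row, or leaves it open which specimen counts. Repeat endoscopies before randomization invite that reading: "If insufficient biopsies have been taken at visit 1 then another endoscopy with biopsy sampling will be done at visit 3", and Table 1 marks visit 4 with the note "Only for subjects with RE LA grade C or D at visits 1 or 3". The protocol does not support it. Section 3.1 treats the investigational week as one collection, which "will allow the collection of baseline data, such as endoscopy with biopsy sampling, 24-hour pH metry, manometry, SAP and laboratory measurements". Section 4.4.3.1 already pools visits 1 and 3 for laboratory samples from that week, and nothing orders table rows by raw visit number. The visit 4 endoscopy is described as a check of esophagitis grade, with no mention of biopsies in that text: "In case of mucosal breaks classified as LA grade C or D at visit 3 a new endoscopy must be done at visit 4". The Table 1 footnote for the visit 1 biopsies is blank and Appendix H is not shown, so no conclusion can rest on them.

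**Conclusion.** The point holds as a minor one. The protocol fixes a marginal summary for a variable that it words as change and lists for safety as well as efficacy, while giving laboratory data the within-subject comparison that histology also needs. Because withdrawal for failure follows different rules in the two arms, by-visit frequencies cannot separate change within subjects from change in who remains.

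The size is unknown. The ranges above (5.7% to 12.1% at 5 years and 4.8% to 15.2% at 10 years, around an unchanged 10%) depend on assumed prevalences, on an assumed link between lesions and failure, on no other losses and, for year 10, on extrapolated retention. They do not estimate what will happen in this trial, and with no link the distortion is zero. The absence of a formal test is a stated choice and is not a fault. Nor does the point imply that serious findings would be missed, since those are reported as serious adverse events.

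**What to change.** In Section 6.2.3, keep the by-visit frequencies and add the following, by arm and for each graded histological variable and biopsy site:

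- a descriptive shift table of baseline against the last available biopsy, including the discontinuation biopsy;
- the same table of baseline against visit 16 and against visit 39;
- for each, the numbers worsened, unchanged and improved among subjects with paired biopsies.

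Adopt for histology the baseline rule in Section 4.4.3.1: visit 3, or visit 1 for untreated subjects. Add no formal test.

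The cost is one sentence on the baseline and some descriptive tables from gradings already sent to the sponsor; no new visit, biopsy or data item is needed. With the four biopsy sites in Section 4.3.4.1 and three comparisons, this is at most 4 × 3 = 12 tables per graded variable, which is why only two scheduled visits are proposed and not all five. The tables are restricted to subjects with paired biopsies. They remove apparent change due to composition, but not selection in who stays.

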### Safety analyses

The laboratory data will be presented in terms of median, Mean and SD for the baseline value, the last visit value and the change from baseline to last visit. A cross-table showing the number of subjects with the values below, within and above the normal range at baseline versus the same classification at the last visit will be provided for each laboratory variable. Graphs showing last visit values versus the baseline values and descriptive presentation over time will be presented for each treatment group and each laboratory variable.

Serious adverse events and AEs causing premature discontinuation of study drug and/or study will be presented descriptively.

#### **6.2.4 Interim analyses**

Interim analyses are planned 3 years (visit 12) and 5 years (visit 16) after last subject randomized. The purpose the interim analyses are to evaluate efficacy and tolerability.

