- All serious adverse events and those adverse events causing premature discontinuation of study drug and/or study will be recorded at each visit except visit 1 and 5 (surgery visit).

During the 10-year study period subjects in both treatment arms having (moderate-severe) recurrent GERD symptoms on at least **3 consecutive days** will be instructed to contact the clinic. The subject will be asked to answer the questions regarding treatment failure and follow the instructions for each treatment arm. In case of dose adjustments, the increased dosage must be taken for 8 weeks before a second dose adjustment is made. A 24 hr pH metry and SAP should be made prior to dose adjustment (only applicable to an adjustment to a higher dose). If the subject is symptom-free and satisfied after this treatment period with an increased dose, a reduction to the previous lower dose should be aimed at. At least one attempt to return to the previous lower dose should be made. After two periods of dose increase due to recurrence of symptoms, the investigator can decide which dose is required to maintain symptoms under control for the remaining study period, but the dose cannot exceed 40 mg o.d. or 20 mg b.i.d.

[figure not shown]
In case of subjects who are satisfied with their treatment, but with temporarily (at least **3 consecutive days**) moderate-severe GERD symptoms, the subject will be offered an endoscopy and:

- Subjects in the medical arm will then receive treatment with esomeprazole 40 mg o.d. for 2-12 weeks according to endoscopic findings and symptomatology. After treatment the subject in the medical arm will continue the study with esomeprazole at a dose which is required to maintain symptoms under control but does not exceed 40 mg daily.
- Subjects in the surgical arm are allowed to have symptomatic treatment (antacids) and will continue the study.

Visits 5 and 6 are only relevant to subjects randomized to surgery.

Interim analyses are planned 3 years (visit 12) and 5 years (visit 16) after last subject randomized (medical arm) or operated (surgical arm) on, to evaluate efficacy and tolerability.

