### 3.2 Rationale for study design, doses and control groups

This study is designed to investigate the efficacy and tolerability of long-term treatment with esomeprazole compared to anti-reflux surgery i.e. laparoscopic fundoplication.

The 12-week run-in period allows for the treatment of reflux esophagitis, enables the initial tolerability to esomeprazole to be controlled and allows for the collection of baseline data.

Dose adjustment not exceeding 40 mg daily will be allowed. Esomeprazole 40 mg o.d. has been chosen for during the run-in period. This dose has been shown to be the most effective in the healing of reflux esophagitis (Richter JE et al 2001).

Laparoscopic fundoplication is the surgical method chosen to be the comparator to long-term medical treatment (for surgical details see Section 3.4.2).

The duration of the study is 10 years. The target population is adult subjects with chronic gastroesophageal reflux disease in need for either long-term medical treatment or surgical treatment. All subjects should be eligible for surgery. The subjects will be randomized to either medical treatment or anti-reflux surgery.

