## **6. STATISTICAL METHODS AND DETERMINATION OF SAMPLE SIZE**

### **6.1 Determination of sample size**

The true rate of treatment successes (i.e. subjects who have not experienced treatment insufficiency within 5 years) is assumed to be at least 70% for both treatments. With 275 subjects on each treatment the true difference between treatment is, with a probability of 95%, not going to differ by more than 8 percentage points from the observed difference.

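### The protocol does not fix which efficacy analysis is confirmatory: Section 6.1 sizes the trial on 5 years, Section 6.2.4 calls the 5-year analysis interim, and the study runs 10 years

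*Protocol*

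**What the plan says.** - **Test.** Section 6.2.3 compares the arms on time to treatment failure by "a log rank test (two-sided) for statistical inference". The primary row of Table 3 gives "Logrank test, and survival curves". Neither attaches an analysis time, although the Table 3 column for the summary statistic is meant to carry one.
- **Looks.** Section 6.2.4: "Interim analyses are planned 3 years (visit 12) and 5 years (visit 16) after last subject randomized". It adds: "The purpose the interim analyses are to evaluate efficacy and tolerability". No test, level, boundary or stopping rule follows, and no statement that these looks are descriptive.
- **Cut-off, second wording.** Section 3.1 dates the same looks "after last subject randomized (medical arm) or operated (surgical arm) on, to evaluate efficacy and tolerability".
- **Sizing.** Section 6.1 counts as successes "subjects who have not experienced treatment insufficiency within 5 years". The rate "is assumed to be at least 70% for both treatments", and 275 subjects per arm are to give a 95% precision of 8 percentage points.
- **Length.** Section 3.2: "The duration of the study is 10 years". The title also gives 10 years. Section 3.1 describes a 5-year trial with a 5-year prolongation, Section 3.2.1 presents the prolongation as extra follow-up after a 5-year comparison, and a footnote to Table 2 makes visit 16 the last visit of the 5-year study.

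**The concern.** Two horizons compete. The sizing, the design description and the Table 2 footnote point to 5 years. The title, the stated duration and the interim label on the 5-year analysis point to 10. So the analysis for which the trial was sized is called interim, and the implied 10-year final analysis has no sizing of its own.

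The single logrank has no date, so it could be run and reported at 3, 5 or 10 years. If the results disagreed, the protocol gives no rule for which one stands. If a significance claim could be made at any look, the level of each separate test would not be the error rate of the trial.

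**Working it through.** **1. The plan's own figure.** Inputs from Section 6.1: 70% success, 275 per arm, 95% confidence.

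Half-width = 1.96 × √(2 × 0.70 × 0.30 / 275) = 7.66 points. Adding a continuity correction of 1/275 gives 8.02. The stated 8 points is reproduced. It is a precision statement at 5 years and sets no significance level.

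**2. Information at each look.** Assume a constant hazard that gives 70% success at 5 years: λ = −ln(0.70)/5 = 0.0713 per year. The failure proportion is F(t) = 1 − exp(−λt), and there are 550 subjects.

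| Look | F(t) | Events | Fraction of final events |
|---|---|---|---|
| 3 years | 0.193 | 106 | 0.378 |
| 5 years | 0.300 | 165 | 0.588 |
| 10 years | 0.510 | 280 | 1 |

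**3. Overall type I error.** Assume a two-sided 5% logrank at each look and a claim allowed at any. Under no difference, the three statistics are jointly normal with correlation √(tᵢ/tⱼ), where t is the information fraction:
- years 3 and 5: √(0.378/0.588) = 0.80
- years 3 and 10: √0.378 = 0.61
- years 5 and 10: √0.588 = 0.77

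P(at least one |Z| > 1.96) = 10.5%. For years 5 and 10 alone it is 8.0%, and for years 3 and 5 alone 7.8%. Treating the looks as independent (1 − 0.95³ = 14.3%) or adding the levels (15%) would overstate it, because the looks share data.

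**4. Sensitivity to inputs that the protocol does not give.** Three looks; each range is an assumption.

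| Input varied | Overall error |
|---|---|
| Dropout 0 to 10% per year, with or without 1 year of staggered accrual | 9.4 to 10.5% |
| Uptake of the prolongation 40 to 100% | 9.7 to 10.5% |
| Weibull shape 0.4 to 1.5 | 8.7 to 11.4% |
| 5-year success 70 to 90% | 10.5 to 10.8% |

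**5. What would hold 5% across three looks.** With the fractions in step 2, an equal nominal level of about 0.0225 at each look would do so. O'Brien-Fleming-type spending would give about 0.0014, 0.0101 and 0.0458. One confirmatory test with the other looks descriptive also holds 5%.

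**6. Section 6.1 at 10 years.** The same constant hazard gives 0.70² = 49% success. The half-width is then 1.96 × √(2 × 0.49 × 0.51 / 275) = 8.4 points with complete follow-up. Entry to the prolongation is by agreement at visit 16, so the real figure would be wider.

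**The case against.** The strongest reply is that the protocol never says the logrank is run at each look. Evaluating efficacy could mean life-table curves and estimates. No significance level appears anywhere, since the 95% in Section 6.1 concerns precision. The declared aim is to estimate, nothing provides for an early claim, and the interim label can be read as pointing to a single final test at 10 years, which would keep its level. Section 6.2.1 announces a statistical analysis plan, which is not among the documents at hand and may hold an alpha rule. The two horizons also have a natural origin: a 5-year design that was later extended.

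Most of this stands. A reader might infer that the trial will test at 5% three times and so has a 10% error rate. The documents do not support that as fact, only as a conditional. The extension explains the conflict but does not resolve it, because the current text still does not say which analysis is confirmatory.

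Three further inferences are tempting but unsupported:
- That early results would influence later classification of failures in this open trial. No passage says that interim efficacy results go to the investigators.
- That the analysis plan may be written after the interim looks. Section 6.2.1 ties it to database lock without saying which lock.
- That the two cut-off wordings affect the error rate. They differ by at most about the 3 months allowed between randomization and surgery, and Section 4.3.2.1 counts event time from start of treatment. The mismatch needs only reconciling.

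**Conclusion.** The point holds as a contradiction about the confirmatory horizon, together with efficacy looks whose inferential status is left open. The trial is sized on 5 years, the 5-year analysis is called interim, the study ends at 10 years, and the one primary test is tied to none of these times.

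The possible cost is an overall type I error of about 10%, roughly 9 to 11% over the inputs varied, or about 8% if only years 5 and 10 count. That size rests on three assumptions that the protocol does not state: a two-sided 5% level, the logrank at every look, and freedom to claim at any look. If the 3- and 5-year looks are descriptive, the final test keeps its level and only the conflict over the horizon remains. The change should be made: it is cheap and settles the question either way.

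**What to change.** - **Name one analysis.** In Section 6.2.4 and the primary row of Table 3, name one confirmatory logrank at two-sided 5%. The 5-year analysis matches Section 6.1. If the sponsor prefers 10 years, say so and restate Section 6.1 for that horizon, allowing for prolongation uptake and discontinuation.
- **Settle the other looks.** Report them as Kaplan-Meier estimates with 95% confidence intervals and no significance claim. Otherwise state an alpha-spending rule covering every look at which a claim is allowed.
- **Reconcile the cut-off.** Use one wording in Sections 3.1 and 6.2.4.
- **Base the choice on the design.** Section 7.8 puts the last subject in at Q4 2002, so the 3-year point falls around Q4 2005, before the prolongation starts in Q1 2007. That look may already be past, so the choice should rest on Section 6.1 and not on any result.

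The cost is protocol and analysis-plan wording. Naming the 5-year analysis changes neither conduct nor sample size. The downside is that no formal significance claim is available at the non-confirmatory looks, or, under spending, that each look is tested at a stricter level.
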